Project code	EpidProtect-21
Study title	Exhaustive, cross-sectional, non-interventional, multicenter retrospective epidemiological study of the COVID-2019 incidence and prevention methods of SARS, including COVID-2019, among staff of participating organizations.
Version of Synopsis	0.2, 15.02.2021.
Justification of study	
Coronaviruses are a large family of viruses that might cause illness in animals or humans. SARS-CoV-2 is an enveloped, single-stranded RNA virus of the β genus. It can cause respiratory illness named COVID-19, the severity of which varies from asymptomatic to severe, and which can lead to the patient's death or long-term consequences (so-called post-COVID syndrome). The virus has spread globally and been declared a Public Health Emergency of International Concern by WHO in January 30, 2020.
 
The first case of COVID-19 in Ukraine was detected in early March, 2020. 1273475 cases of the disease have been registered in Ukraine as at February 15, 2021.
 
Quarantine restrictions and other anti-epidemic measures established in Ukraine and their results are the subject of wide debate.
 
Own anti-epidemic measures, in addition to those established by the Government, have also been implemented by numerous representatives of the public sector, non-governmental organizations and business.
 
The company management of the participating organizations decided to provide their staff with prophylactic tools and recommendations for COVID-19 prevention.
 
The study aims to identify the incidence, characteristics of cases and their relationship with the preventive measures used.

Study design	Exhaustive, cross-sectional, non-interventional, multicenter retrospective epidemiological study, case study.
Number of subjects	3443 subjects.

Location of study conduct	
Each subject will participate in the study in the participating organization by which the subject is employed:
 
• SI National Institute of Phthisiology and Pulmonology named after F.G. Yanovsky.• Yuria-Pharm LLC.• Infuzia PJSC.• Institute Hyalual LLC.• Medical Center M.T.K. LLC.• InterChem SLC.• Diatom LLC. 
For the study the following facilities will be organized at each participating organization:
 
• Specially designated locations for material collection and conduction of rapid ELISA tests for the antibodies to COVID-2019.• Specially designated computerized places for questionnaires with assigned staff who organize the order and accuracy of the questionnaire conduct.
Duration of data collection	3 months.
Purpose of the study	To determine the relationship between the systematic use of prophylactics to prevent SARS, including COVID-2019, and the risks of incidence and serious complications of COVID-2019 among staff of participating organizations.
Study objectives	
• To investigate the incidence of COVID-2019 cases in participating organizations.• To investigate the severity of the COVID-2019 cases in participating organizations.• To explore the prevention methods used by staff members.• To determine the relationship between the used prevention methods and incidence of COVID-2019 among staff of participating organizations.

	
• To determine the relationship between the presence of comorbidities, such as bronchial asthma and COPD, and the incidence/severity of COVID-2019.• To determine the relationship between the COVID-2019 case and the course of comorbidities, such as bronchial asthma and chronic obstructive pulmonary disease (COPD).• To identify the relationship between different strategies and combinations of drugs used for prophylactics at any time from March 2020 and the risk of having a COVID-2019 case.• To identify the relationship between different strategies and combinations of drugs used for prophylactics at any time from March 2020 and the risk of having a severe COVID-2019 case.• To identify the relationship between different strategies and combinations of drugs used for prophylactics at any time from March 2020 and the risk of hospitalization of persons who had at least one COVID-2019 case.
Methodology	
Each subject will be assigned an individual number, which will be used for conduction of a rapid ELISA test for the antibodies to COVID-2019. Subjects will be notified of the test results.
 
The questionnaires will be conducted when the subject enters the data in the electronic case report form after signing the consent to processing of personal data.
 
For the purposes of analysis, the subject enters his individual number in the questionnaire, as well as number of a rapid ELISA test for antibodies to COVID-2019 and its result. The entered data will be compared with the databases which contain the results of rapid ELISA tests.
 
The questionnaire includes questions related to the main risks and protective factors of the COVID-2019 disease: demographic, anthropometric data, lifestyle data, prophylactics methods, subject's costs spent on COVID-2019 prophylactics.

	
For subjects who had the COVID-2019 case, a separate block of questionnaire was created to collect data on prophylactics, treatment of COVID-2019 case, the course of the disease and the consequences of the disease case, as well as costs spent on COVID-2019 treatment.
 
The completeness of entered data in the electronic case report form will be controlled by specially designated authorized persons in each participating organization, who were designated by the person responsible for conducting the study in each participating organization.
 
The correctness of data entered in the electronic case report form will be controlled by remote monitoring.
 
The questionnaire cannot be completed until all required fields of the case report form have been completed.
 
A structured description of the available medical documentation for fatal cases of COVID-2019 will be conducted separately.
 
Demographic, anthropometric data, lifestyle data, prophylactics methods, treatment of COVID-2019, the course of the COVID-2019 case will be described.

Duration of each subject's participation in the study	1,5-2 hours.
Visit schedule	
Visit 1. Conducting of a rapid ELISA test.
 
Visit 2. Online questionnaires among staff of participating organizations.

Study endpoints	
• The incidence of COVID-2019 cases in participating organizations.• The severity of the COVID-2019 cases in participating organizations.• Prevention methods of SARS, including COVID-2019, which were used by subject who had at least one COVID-2019 case.

	
Prevention methods of SARS, including COVID-2019, which were used by subject who did not have any COVID-2019 case.Relationship between the used prevention methods and incidence of COVID-2019 among staff of participating organizations.Relationship between the presence of comorbidities, such as bronchial asthma and COPD, and the incidence/severity of COVID-2019 case.Relationship between the COVID-2019 case and the course of comorbidities, such as bronchial asthma and chronic obstructive pulmonary disease (COPD).Relationship between different strategies and combinations of drugs used for prophylactics at any time from March 2020 and the risk of having a COVID-2019 case.Relationship between different strategies and combinations of drugs used for prophylactics at any time from March 2020 and the risk of having a severe COVID-2019 case.Relationship between different strategies and combinations of drugs used for prophylactics at any time from March 2020 and the risk of hospitalization of subjects who had at least one COVID-2019 case.
Study variables	
Demographic characteristics: age, gender.Anthropometric characteristics: body weight, height.Blood group.Number of people in the household.Lifestyle: the presence of bad habits, physical activity, diet.Medical history: comorbidities, their treatment.Prevention methods of SARS, including COVID-2019, currently used by the subject.Number of COVID-2019 cases, which subject had.Characteristics of the disease case, its treatment.

	
Prevention methods of SARS, including COVID-2019, which were used by subject who had at least one COVID-2019 case.Prevention methods of SARS, including COVID-2019, which were used by subject who did not have any COVID-2019 case.Amount of costs spent on prevention and treatment of SARS, including COVID-2019.Relationship between different strategies and combinations of drugs used for prophylactics at any time from March 2020 and the risk of having a COVID-2019 case.Relationship between different strategies and combinations of drugs used for prophylactics at any time from March 2020 and the risk of having a severe COVID-2019 case.Relationship between different strategies and combinations of drugs used for prophylactics at any time from March 2020 and the risk of hospitalization of subjects who had at least one COVID-2019 case.
Inclusion criteria	Subjects who meet all the inclusion criteria will be included in the study: 
The subject gave the consent to participate in the study and signed the consent to processing of personal data.The subject aged 18 years and older.The subject is employed by one of the participating organizations.
Exclusion/withdrawal criteria	The nature of the study does not provide for withdrawal criteria. The subject may not be included in the study due to non-compliance with the inclusion criteria or due to force majeure.
Calculation of sample size	Not applicable as it is exhaustive study. Participating organizations undertake to organize the involvement in the study of at least 95% of persons employed by participating organizations.

Study limitations	
Persons, who were employed by one of the participating organizations from March 1, 2020, but who do not have employment relations with the participating organizations during the study period or persons who are on maternity leave, will not be included in the study.
 
Another study limitation is duration of data collection (due to long-term data collection there is a difference in the duration of action of the exposure factor).
 
The retrospective study design has limitations on the completeness and accuracy of the data provided by the study subjects.
 
There may be difficulties in filling in the missing data.
 
Certain relationships can be difficult to describe.
 
The direction of the relationship cannot be determined for all relationships (there may be an inverse relationship).
 
Potential data distortion may be due to the subject selection; use of an electronic data collection system; possible low computer literacy of some subjects; lack of data verification and query generation.
 
The completeness and correctness of the description of available medical documentation for fatal cases of COVID-2019 depends on the amount of information provided and its quality. Conclusions from it cannot be extended to other population members.

-------------------	---

Statistical analysis plan

In the context of this data analysis, all the main steps from the primary data to the results of the study will be described separately in the Statistical Analysis Plan.

This study is not intended to accept or reject pre-defined hypotheses, thus statistical analysis will mainly be descriptive.

All types of analysis will be done for the entire available study population with available data.

If there is a sufficient amount of data in the subpopulations, a separate statistical analysis will be performed.

No conditional calculation methods will be applied to the missed values.

The statistical generalization will consist of frequency tables of categorical variables (number, %).

For metric variables, descriptive statistics (number of subjects with available observations, number of missed values, mean, standard deviation, median, 25th and 75th percentiles, minimum and maximum) will be presented in tabular form.

Statistical conclusions will be used to assess the potential relationship between the identified variables and the incidence / severity of COVID-2019.

The relationship between the subject's characteristics and the variables of interest will be assessed using a one-dimensional and multidimensional (polynomial) logistic regression model for variables, which have no more than 20% omitted data.

The final model will be selected with a view to minimizing the Akaike information criterion value.

2×2 tables, χ^2 -square were used for calculations of odds ratios.

Rough odds ratios and adjusted odds ratios with corresponding 95% confidence intervals and p-values will be generated and presented for both one-dimensional and multidimensional logistics models.

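### The purpose concerns systematic use of prophylactics, but no objective, endpoint or listed variable carries regularity or timing of use, so the odds ratios may not answer it

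*Combined protocol and SAP*

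**What the plan says.** All references are to the combined protocol and SAP.

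- **Purpose of the study:** the aim is given as "To determine the relationship between the systematic use of prophylactics to prevent SARS, including COVID-2019, and the risks of incidence and serious complications". This is the only place where use is qualified as systematic, and no definition is given.
- **Study objectives and Study endpoints:** the general endpoint is "Relationship between the used prevention methods and incidence of COVID-2019 among staff of participating organizations". The first of three drug endpoints is "Relationship between different strategies and combinations of drugs used for prophylactics at any time from March 2020 and the risk of having a COVID-2019 case"; the other two have the same exposure wording, with severe case and hospitalisation as outcomes. None sets a minimum frequency or duration, and the strategies are not described.
- **Study variables:** "Prevention methods of SARS, including COVID-2019, currently used by the subject", the methods used by subjects with and without a case, and the costs of prevention and treatment. Frequency, duration and start date of use are not listed.
- **Methodology:** the questionnaire is described by topic only. Subjects who had a case complete an additional block that also covers prophylactics.
- **Statistical analysis plan:** odds ratios come from 2×2 tables and logistic regression, crude and adjusted, with 95% confidence intervals and p-values. The coding of exposure is not given, and the detailed steps are left to a separate document.

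**The concern.** The exposure named in the purpose differs from the exposure that the endpoints and variables describe. Someone who took a product for two days and someone who took it throughout both satisfy the wording of the drug endpoints. If nothing else separates them, they share an exposed group and the odds ratio describes any use.

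This is a question of intensity of exposure, and it remains even if all counted use precedes illness. A result near 1 could then mean that systematic use does nothing, or that its effect was averaged with that of occasional use. A result away from 1 could not be credited to systematic use either. Without regularity data, a gradient across levels of use could not be examined, and such a gradient would be useful support for an observational claim about prophylaxis.

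**Working it through.** **The plan's own figures.** There is no calculation to reproduce. The number of subjects is "3443 subjects", a headcount, and the entry for sample size is "Not applicable as it is exhaustive study". No risk, effect size, alpha or power is stated. Every rate and odds ratio below is an assumption for illustration.

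**Step 1: occasional use has no effect.** Assume risk 0.20 in non-users (odds 0.25) and an odds ratio (OR) of 0.50 for systematic use.

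- Systematic users: odds 0.25 × 0.50 = 0.125; risk 0.125/1.125 = 0.111.
- If a share f of users is occasional, the risk in all users is f × 0.20 + (1 − f) × 0.111.
- Any-use OR = [risk/(1 − risk)]/0.25.

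| Share of users occasional | Risk in all users | Any-use OR |
|---|---|---|
| 25% | 13.3% | 0.62 |
| 50% | 15.6% | 0.74 |
| 75% | 17.8% | 0.86 |

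**Step 2: vary the effect of occasional use.** Keep the 20% risk, take an OR of 0.60 for systematic use (odds 0.15, risk 0.130), and let half the users be occasional.

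| OR for occasional use | Risk in occasional users | Risk in all users | Any-use OR |
|---|---|---|---|
| 1.0 | 20.0% | 16.5% | 0.79 |
| 0.70 | 14.9% | 14.0% | 0.65 |
| 0.40 | 9.1% | 11.1% | 0.50 |

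The first row shows clear attenuation and the second little. In the third the pooled value lies further from 1 than the OR for systematic use. With non-user risks of 10% to 30%, the first row stays between 0.787 and 0.796.

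**Step 3: what separation would gain.** Assume that half of 3443 subjects are users, an OR of 0.60 for systematic use, an OR of 1.0 for occasional use and two-sided alpha 0.05. Power is Φ[(|p0 − p1| − 1.96 × SE0)/SE1], where SE0 uses the pooled risk and SE1 the separate risks.

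- Half the users systematic: any use against none, 75%; systematic against none, above 99%.
- A quarter of the users systematic: 25% (any-use OR 0.89) against 93%.

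**Step 4: why timing must enter the definition.** Suppose no true effect, 20% risk, and half the subjects users before any case. As fractions of all subjects, there are 0.10 cases and 0.40 non-cases in each half.

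- If 10% of non-user cases start use afterwards and are counted as users: OR = (0.11 × 0.40)/(0.40 × 0.09) = 1.22. With 30%: (0.13 × 0.40)/(0.40 × 0.07) = 1.86.
- If instead 10% of non-user non-cases start late, having had longer to do so: OR = (0.10 × 0.36)/(0.44 × 0.10) = 0.82. With 30%: (0.10 × 0.28)/(0.52 × 0.10) = 0.54.

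A regularity rule that ignores timing could therefore produce an apparent effect in either direction.

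**The case against.** The document is a synopsis, and the questionnaire items are not reproduced. The form may already ask about regularity, and the extra block for cases does collect something on prophylaxis. The undefined strategies could be meant to separate regular from one-off use, and logistic regression can take more than two exposure levels. Costs are collected and could serve as a crude marker of intensity. Study limitations admits that exposure duration differs and that recall is imperfect. The plan also says: "This study is not intended to accept or reject pre-defined hypotheses, thus statistical analysis will mainly be descriptive".

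Much of this stands. A reader might infer that exposure is coded as ever against never, that one-off and regular users are certainly pooled, that the association is certainly diluted, and that no gradient could be examined. The documents do not support this. No coding is stated, the time window does not itself define ever-use, and the absence of a listed variable does not prove the absence of a questionnaire item.

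The objection does not close the gap:

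- A later analysis document cannot recover frequency or timing that was not collected.
- If regularity is asked only in the block for cases, non-cases lack the comparable data.
- Cost is a weak proxy, because Justification of study says that management decided to supply staff with prophylactic tools; a regular user may have spent nothing.
- The admitted difference in duration is attributed to the length of data collection, not to regular against one-off use.
- A mainly descriptive study that reports adjusted odds ratios with p-values still needs an exposure that matches its question.

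**Conclusion.** The concern holds as a mismatch between the purpose and the exposure as specified. Followed as written, the listed variables cannot isolate systematic use, so the reported odds ratios may not answer the stated purpose.

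The size is conditional. The range of 0.62 to 0.86 requires the assumed 20% risk, an OR of 0.50 for systematic use and no effect at all of occasional use. It should not be read as the expected bias, nor attenuation as its certain direction: Step 2 gives anything from marked attenuation to a pooled value further from 1, depending on the effect of occasional use. The firm conclusion is that neither a null nor a positive result could be attributed to systematic use unless regularity is recorded and classified.

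**What to change.** **Data.** If the questionnaire does not already do so, record for each prophylactic the usual frequency of use and the start and stop month. Put the same items to cases and non-cases, in the common part of the form.

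**Definition.** Before analysis, define each strategy and fix a rule that classifies every subject as a systematic, occasional or non-user. Base it mainly on frequency. Count only use before the first COVID-2019 case and, for non-cases, use within a comparable at-risk window. Do not base it on total months accumulated: cases have a shorter window before illness, so such a rule could make systematic use look protective when it is not.

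**Reporting.** For the case, severe-case and hospitalisation endpoints, show systematic and occasional use each against non-use, alongside the any-use contrast. This needs no formal hierarchy of hypotheses.

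**Cost.** A few more items per prophylactic and some added analysis wording. The questionnaire becomes slightly longer, the analysis relies more on recall (which may differ between cases and non-cases), and the exposure groups are smaller.

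### Staff know their antibody result when they report prophylaxis and illness history; locking those answers first is a cheap guard against an avoidable, probably small, source of differential reporting

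*Combined protocol and SAP*

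**What the plan says.** The Visit schedule puts the rapid ELISA at Visit 1, followed by "Visit 2. Online questionnaires among staff of participating organizations". Under Methodology, "Subjects will be notified of the test results", and each subject enters an individual number in the questionnaire, "as well as number of a rapid ELISA test for antibodies to COVID-2019 and its result". Results are also held elsewhere: "The entered data will be compared with the databases which contain the results of rapid ELISA tests".

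The same form records prophylactic methods. It then has a further part: "For subjects who had the COVID-2019 case, a separate block of questionnaire was created to collect data on prophylactics", together with treatment, course and consequences. Study variables include "Number of COVID-2019 cases, which subject had". No section defines a case.

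One of the Study objectives is the relationship between strategies and drug combinations "used for prophylactics at any time from March 2020 and the risk of having a COVID-2019 case". Study limitations concedes that "The retrospective study design has limitations on the completeness and accuracy of the data provided by the study subjects". It also admits missing verification and relationships whose direction cannot be settled. It does not mention reporting that depends on a result the study itself has disclosed.

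**The concern.** The time of notification is not stated, but nobody can enter a result they do not know. Serostatus is therefore known by the time that field is filled, in the form that asks what prophylaxis was used. The study's purpose is the association between that self-reported use and COVID-2019. If knowing the result changes the report, exposure is misclassified differently in cases and non-cases.

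Nothing downstream repairs this. The database comparison checks the entered test data, not reported prophylaxis. The logistic models adjust for recorded covariates and cannot correct exposure reports that depend on the result. Ordinary recall error comes with any retrospective design; this component is created by the visit order.

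Its reach is limited. Disclosure can only affect staff who learn something new from the test. Staff with a recognised illness already knew, so most of the severity and hospitalization analyses are unaffected.

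**Working it through.** The documents give no figure to reproduce: 3443 is a census count with no power calculation, and no recall, prevalence or usage figures are stated. The following is an illustration on assumed inputs.

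**Assumptions.** True OR 1; no false reports of use; recall of true use a = 0.85 in staff who know they were infected and b = 0.95 in all others; I = 0.30 infected; u = 0.30 of infections unrecognised before the test; true use p = 0.5 or 0.7. Newly informed staff are given the same recall as staff who already knew. Staff who were ill but test seronegative are not modelled.

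**Formula.** odds(x) = x/(1 − x); OR = odds(p·s_case)/odds(p·s_noncase), where s is recall of true use in each group.

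1. *Cases include serology-detected infections.* With disclosure, s_case = 0.85. Without, s_case = 0.7 × 0.85 + 0.3 × 0.95 = 0.88. In both, s_noncase = 0.95.
2. *Self-reported cases; newly informed seropositives relabel themselves as cases.* With and without disclosure, s_case = 0.85 and s_noncase = 0.95.
3. *Self-reported cases; newly informed seropositives stay non-cases.* Without disclosure as in (2). With it, their share of non-cases is w = 0.09/(0.09 + 0.70) = 0.114, so s_noncase = 0.114 × 0.85 + 0.886 × 0.95 = 0.939.

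| Scenario | Use | OR with disclosure | OR without | Factor |
|---|---|---|---|---|
| 1 | 50% | 0.817 | 0.868 | 0.94 |
| 1 | 70% | 0.740 | 0.808 | 0.92 |
| 2 | 50% | 0.817 | 0.817 | 1.00 |
| 2 | 70% | 0.740 | 0.740 | 1.00 |
| 3 | 50% | 0.836 | 0.817 | 1.02 |
| 3 | 70% | 0.767 | 0.740 | 1.04 |

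For the first row: odds(0.425)/odds(0.475) = 0.739/0.905 = 0.817 and odds(0.44)/odds(0.475) = 0.786/0.905 = 0.868.

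**Sensitivity of the factor (50% use; 70% use).**
- u from 0.1 to 0.5: scenario 1 runs 0.98 to 0.90; 0.97 to 0.86. Scenario 3 runs 1.01 to 1.04; 1.01 to 1.06.
- I from 0.2 to 0.4: scenario 3 runs 1.01 to 1.03; 1.02 to 1.05.
- Recall 90% against 95%: scenario 1 gives 0.97; 0.96. Scenario 3 gives 1.01; 1.02.
- Recall reversed, 95% against 85%: scenario 1 gives 1.06; 1.10. Scenario 3 gives 0.98; 0.97. The direction flips.

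**What remains without disclosure.** In scenario 1, ln 0.868/ln 0.817 = 0.70 of the log-OR bias at 50% use, and 0.71 at 70%. In scenarios 2 and 3 all of it remains.

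**Scale.** With 3443 subjects, 30% cases and 50% use, SE(log OR) = 1/√(3443 × 0.3 × 0.7 × 0.25) = 0.0744, so the 95% interval around OR 1 is 0.86 to 1.16. Every base-case factor lies inside it.

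**The case against.** The strongest case against reordering uses the same model. Asking about cases both in the number of cases and in a separate block suggests self-report, which is scenario 2 or 3. There, testing last gains nothing or leaves the OR slightly further from 1 (0.84 to 0.82; 0.77 to 0.74). This stands: the modelled gain depends on the case definition, which the documents do not give. But in scenario 3 disclosure helps only because it happens to offset another bias, which is no reason to keep it.

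Locking the whole form before the test would also have a cost. Infections first detected by the ELISA, about 3443 × 0.30 × 0.30 = 310 staff under the assumptions, could not reach the case block or be self-reported as cases. With a true OR of 0.70, 50% use in the uninfected and no recall gap, leaving them among the non-cases moves the scenario 2 OR from 0.70 to 0.73; with the 85%/95% gap it moves from 0.60 to 0.62. This also stands against a whole-form lock, but not against locking only the prophylaxis and prior-illness answers.

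It can also be said that Study limitations already covers the matter and that the analysis is mainly descriptive. The admission is general and does not name this source, and odds ratios with confidence intervals and p-values will still be reported. That the factors lie within sampling error does not make them harmless, because the interval does not allow for systematic error.

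**Conclusion.** The point holds as an avoidable weakness in the order of data collection, and not as a demonstrated large bias. On the stated assumptions, disclosure multiplies the odds ratio by about 0.92 to 0.94 if serology-detected infections count as cases and by about 1.00 to 1.04 if cases are self-reported. The inputs are assumed, and reversing the recall gap reverses the direction.

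A reader might infer that disclosure explains the whole recall gap and that reordering restores an unbiased odds ratio. A calculation on that basis, with 80% recall in seropositives against 90% in seronegatives, 20 to 40% seropositive and 30 to 70% use, gives apparent odds ratios of 0.85 to 0.75 and nominal significance in about 36 to 98% of studies, and exactly 1.00 once recall is equal. The documents do not support this reading. Staff with a recognised illness, or an earlier test, knew before Visit 1, and visit order does not change their recall. Nor do the documents support saying that reordering helps under every case definition.

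The change is worth making because it is cheap and removes one source of differential exposure reporting that nothing else in the plan addresses.

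**What to change.** - Have the prophylaxis questions and the history of already recognised illness completed and locked before the test, or at least before the result is disclosed. Done before the test, no available result is withheld.
- Take the antibody result from the ELISA database by individual number, and record the test number at testing as the linkage check. If a self-entered result is still wanted, collect it after the lock.
- After the result, keep the separate case block open for newly detected infections and flag those entries as post-disclosure.
- Use the locked prophylaxis answers as the exposure in the odds-ratio analyses.
- Add residual differential recall, by known illness or earlier testing, to Study limitations.

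This needs no extra subjects or tests. It costs a two-part form with a lock, slightly later notification, and a changed self-entry cross-check against the database. Staff who attend only once would have a missing antibody result instead of a missing questionnaire.

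### The endpoint relating a COVID-19 case to the course of asthma/COPD has no matching outcome variable, and no course data are described for staff with these diseases who had no case

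*Combined protocol and SAP*

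**What the plan says.** Study objectives includes "To determine the relationship between the COVID-2019 case and the course of comorbidities, such as bronchial asthma and chronic obstructive pulmonary disease (COPD"), and Study endpoints repeats it in almost the same words: "Relationship between the COVID-2019 case and the course of comorbidities, such as bronchial asthma and chronic obstructive pulmonary disease (COPD"). Neither place gives a measure, a time window or a definition of course.

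Under Study variables, the entry on comorbidities is "Medical history: comorbidities, their treatment". A separate entry, "Characteristics of the disease case, its treatment", describes the COVID-19 episode.

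Methodology describes two sets of questions:
- **For everyone:** "The questionnaire includes questions related to the main risks and protective factors of the COVID-2019 disease: demographic, anthropometric data, lifestyle data, prophylactics methods", plus what the subject spent on prophylaxis.
- **For cases only:** "For subjects who had the COVID-2019 case, a separate block of questionnaire was created to collect data on prophylactics". This block also covers treatment, "the course of the disease and the consequences of the disease case", and treatment costs.

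Study design calls the study "Exhaustive, cross-sectional, non-interventional, multicenter retrospective epidemiological study, case study". Visit schedule has one antibody test and one online questionnaire. The Statistical analysis plan section directs its inference at the incidence and severity of COVID-19. It does not name the course of a comorbidity as an outcome.

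**The concern.** The objective just before this one asks whether having asthma or COPD is related to getting COVID-19 or to its severity. For that, presence of the disease is enough. This objective runs the other way: the COVID-19 case is the exposure, and what happens to the asthma or COPD is the outcome. A relationship in that direction needs the outcome in people with and without the exposure.

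Both diseases fluctuate and can worsen without COVID-19. A proportion of cases reporting worse disease control therefore says little until it is set against staff with the same diseases and no case over a comparable period. With a single questionnaire, an item not asked of the non-cases cannot be recovered at the analysis stage. What is at stake is whether this endpoint can be reported as a relationship at all.

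**Working it through.** The plan gives no figure for this endpoint, so there is none to reproduce. The check is to set what the endpoint needs beside what the document describes.

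| Needed | Described |
|---|---|
| People with asthma/COPD, with and without a case | Yes. Inclusion criteria admit any consenting adult employee, and the comorbidity entry is not limited to cases |
| A measure of course (exacerbations, control, change in treatment) | None listed. Comorbidities and their treatment only |
| The same measure in cases and non-cases | None described. Course and consequence questions are for cases and concern COVID-19 |
| A reference date or repeat measurement | None. One questionnaire, no follow-up |
| An analysis with course as the outcome | Not named. The regression text refers generally to variables of interest |

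The people are there; the outcome is not. Treatment of the comorbidity could at most be a crude proxy. The document does not define it as a measure of course and does not describe recording change over time.

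**Illustration of size.** The document gives 3443 subjects. It does not give the number with asthma/COPD or the share of staff who had a case. Assume 4% to 8% have asthma/COPD and 25% had a case, with half and double that share (12.5% and 50%) as a range.

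- With asthma/COPD: 3443 × 0.04 = 138; 3443 × 0.08 = 275.
- Cases at 25%: 34 to 69. Non-cases: 103 to 207. (Each count is rounded separately.)

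Suppose 20% of cases report worsening. The risk difference is 20% − 20% = 0 if the background rate is 20%, and 20% − 5% = 15 points if it is 5%. This ambiguity is the same whatever the share of cases.

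If the outcome were collected from everyone, the approximate 95% half-width for a 20% versus 5% comparison is 1.96 × √(0.20 × 0.80/n₁ + 0.05 × 0.95/n₀), with n₁ cases and n₀ non-cases:

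| Asthma/COPD | Case share | n₁ / n₀ | Half-width (points) |
|---|---|---|---|
| 4% | 12.5% | 17 / 121 | 19 |
| 4% | 25% | 34 / 103 | 14 |
| 4% | 50% | 69 / 69 | 11 |
| 8% | 12.5% | 34 / 241 | 14 |
| 8% | 25% | 69 / 207 | 10 |
| 8% | 50% | 138 / 138 | 8 |

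In most of these scenarios the comparison would be imprecise but informative. With few cases (17), even a 15-point difference would not be distinguishable from zero.

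**The case against.** The strongest reply is that absence is being inferred from a summary. The document is a synopsis, the questionnaire is not in it, and the analysis steps are deferred to a separate plan. The Methodology description is visibly incomplete: its account of the general questionnaire omits comorbidities, blood group and household size, all of which Study variables lists. Course items could sit under medical history. This stands as a limit. The finding is about what is described, and if such items are already asked of everyone, listing and defining them is all that is needed on collection. It does not remove the point, because the variable list is where an outcome should appear, and it is detailed enough to include blood group.

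A reader might infer more than the text supports, in three ways:
- **That there is no comparison group.** There is: staff with asthma/COPD and no case are enrolled. What they lack is described course data.
- **That asthma/COPD worsening is recorded in the case-only block and need only be moved.** Nothing places it there. The consequences mentioned are those of the COVID-19 case.
- **That a proportion among cases will be reported as an effect of COVID-19.** The endpoint says relationship, and the analysis is called mainly descriptive.

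Study limitations also concedes that some relationships may be hard to describe and that direction may be unclear. Those caveats are general. They do not disclose that the outcome is undefined and not described for non-cases, which is avoidable.

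**Conclusion.** The point holds in limited form. The endpoint has no matching outcome among the listed variables, and no course data are described for staff with asthma/COPD who had no case. On the plan as described, the relationship cannot be estimated against a background rate, and later analysis could not supply the missing answers.

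The size cannot be derived from the document. The 0 versus 15 points and the half-widths of 8 to 19 points rest entirely on assumed prevalence, case share and worsening rates, and they show the nature of the gap rather than measure it. The conclusion also assumes that the unseen questionnaire asks no more about the course of asthma/COPD than the synopsis describes.

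The reach is modest. This is one of nine objectives and lies outside the stated purpose, which concerns prophylactic use and the risks of COVID-19. No prophylaxis result depends on it. The change is worth making because it is cheap and can only be made before the data are collected.

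**What to change.** 1. Add course of asthma/COPD to Study variables, with a definition.
2. Ask a few conditional items of every subject reporting asthma or COPD, whether or not they had a case: whether it was diagnosed before March 2020, the month of each exacerbation and treatment step-up, and self-rated change in control.
3. Name the comparison in the analysis plan: cases versus non-cases among those diagnosed before March 2020. Count only events after the infection date in cases and after a matched or assigned index month in non-cases, or use person-time before and after infection. A plain count of everything since March 2020 will not do, because for someone infected late in the period it would charge exacerbations that preceded infection to COVID-19.
4. If the items cannot be added, restate the objective and endpoint as a description among cases, with no claim of a relationship.

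The cost is a few extra minutes for a minority of subjects and a few lines of text. Recall of months will be imperfect, and intervals are likely to be wide; how wide cannot be known in advance, since the number with asthma/COPD is not given.
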